10.0 INVESTIGATOR'S OBLIGATIONS

The following administrative items are meant to guide the investigator in the conduct of the study but may be subject to change based on industry and government standard operating procedures, working practice documents, or guidelines. Changes will be reported to the IRB but will not result in protocol amendments.

10.1 Confidentiality

All laboratory specimens, evaluation forms, reports, and other records will be identified in a manner designed to maintain subject confidentiality. All records will be kept in a secure storage area with limited access. Clinical information will not be released without the written permission of the subject or legal guardian, except as necessary for monitoring and auditing by Adverum, its designee, regulatory authorities, or the IRB.

The Investigator and all employees and coworkers involved with this study must not disclose or use for any purpose other than conduct of the study any data, record, or other unpublished, confidential information disclosed to those individuals for the purpose of the study. Prior written agreement from Adverum or its designee must be obtained for the disclosure of any said confidential information to other parties.

10.2 Financial Disclosure and Obligations

Investigators are required to provide financial disclosure information to allow Adverum to submit the complete and accurate certification or disclosure statements required under 21 CFR 54. The investigator must provide to Adverum a commitment to promptly update this information if any relevant changes occur during the course of the investigation and for 1 year following the completion of the study.

10.3 Investigator Documentation

Prior to beginning the study, the investigator will be asked to comply with ICH E68.2 and Title 21 of the CFR by providing to Adverum, the following essential documents, including but not limited to:

- IRB approval
- Signed investigator agreement page of the protocol
- Form FDA 1572, fully executed, and all updates on a new fully executed Form FDA 1572
- Curriculum vitae (CV) for the PI and each Sub-investigator listed on FDA Form 1572
- Financial disclosure information to allow Adverum to submit complete and accurate certification or disclosure statements required under 21 CFR 54. The Investigators must provide to Adverum a commitment to promptly update this information if any relevant changes occur during the course of the investigation and for 1 year after the completion of the study.

- IRB-approved ICF, samples of site advertisements for recruitment for this study, and any other written information regarding this study that is to be provided to the subject or legal guardian
- Laboratory certifications and normal ranges for any local laboratories used by the site, in accordance with 42 CFR 493

10.4 Study Conduct

The Investigator agrees that the study will be conducted according to the principles of ICH E6. The investigator will conduct all aspects of this study in accordance with all national, state, and local laws or regulations. Study information from this protocol will be posted on publicly available clinical trial registers before enrollment of subjects begins.

10.5 Adherence to Protocol

The Investigator agrees to conduct the study as outlined in this protocol in accordance with ICH E6 and all applicable guidelines and regulations.

10.6 Adverse Events and Study Report Requirements

By participating in this study the Investigator agrees to submit reports of SAEs according to the time line and method outlined in the protocol. The investigator agrees to submit annual reports to the study site IRB as appropriate.

10.7 Investigator's Final Report

Upon completion of the study, the Investigator, where applicable, should inform the institution; the Investigator/institution should provide the IRB with a summary of the study outcome and Adverum and regulatory authority(ies) with any reports required.

10.8 Records Retention

Essential documents should be retained until [REDACTED] after the last approval of a marketing application in an ICH region and until there are no pending or contemplated marketing applications in an ICH region or [REDACTED] have elapsed since the formal discontinuation of clinical development of ADVM-043. These documents should be retained for a longer period, however, if required by the applicable regulatory requirements or by an agreement with Adverum. It is the responsibility of Adverum to inform the Investigator/institution as to when these documents no longer need to be retained.

10.9 Publications

After completion of the study, the data may be considered for reporting at a scientific meeting or for publication in a scientific journal. In these cases, Adverum will be responsible for these activities and will work with the Investigators to determine how the manuscript is written and edited, the number and order of authors, the publication to which it is to be submitted, and other related issues. Adverum has final approval authority over all such issues.

Data are the property of Adverum and cannot be published without prior authorization from Adverum; but data and publication thereof will not be unduly withheld.

11.0 STUDY MANAGEMENT

11.1 Monitoring

11.1.1 Monitoring of the Study

The clinical monitor, as a representative of Adverum, has the obligation to follow the study closely. In doing so, the monitor will visit the investigator and study site at periodic intervals, in addition to maintaining necessary telephone and letter contact. The monitor will maintain current personal knowledge of the study through observation, review of study records and source documentation, and discussion of the conduct of the study with the investigator and personnel.

All aspects of the study will be carefully monitored by Adverum or its designee for compliance with applicable government regulation with respect to GCP and standard operating procedures.

11.1.2 Inspection of Records

Investigators and institutions involved in the study will permit study-related monitoring, audits, IRB review, and regulatory inspections by providing direct access to all study records. In the event of an audit, the Investigator agrees to allow Adverum, representatives of Adverum, or a regulatory agency such as FDA access to all study records.

The Investigator should promptly notify Adverum [REDACTED] of any audits scheduled by any regulatory authorities and promptly forward copies of any audit reports to Adverum.

11.2 Management of Protocol Amendments and Deviations

11.2.1 Modification of the Protocol

Any changes in this research activity, except those necessary to remove an apparent, immediate hazard to a subject, must be reviewed and approved by Adverum or designee. Protocol Amendments must be submitted to the Investigator's IRB for approval before any subject can be enrolled into an amended protocol.

11.2.2 Protocol Deviations

A protocol deviation is any unintended or unanticipated departure from the procedures and processes as specified in the protocol. A significant protocol deviation occurs when there is nonadherence to the protocol by the subject or Investigator that results in a significant additional risk to the subject. Significant deviations can include nonadherence to entry criteria; enrollment of the subject without prior Sponsor approval; or nonadherence to FDA regulations or ICH GCP guidelines. Any protocol deviation will lead to the subject being withdrawn from the study (Section 4.2).

The Investigator or designee must document and explain in the subject's source documentation any protocol deviation. The Investigator may implement a deviation from the protocol to eliminate an immediate hazard to a study subject without prior IRB approval. As soon as possible after such an occurrence, the implemented deviation or change, the reasons for it, and any proposed protocol amendments should be submitted to the IRB for review and approval, to Adverum for agreement, and to the regulatory authorities, if required.

Protocol deviations are to be documented by the clinical monitor throughout the course of monitoring visits. PIs are to be notified in writing by the monitor of deviations. The IRB should be notified of all protocol deviations in a timely manner.

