3.6 Dose-Limiting Toxicity and Maximum Tolerated Dose

The first treated subject in a Cohort will be considered the sentinel subject. The proposed dosing interval is at least 14 days between the sentinel and second subject to be dosed, provided there are no safety concerns in the sentinel subject prior to dosing the next subject.

A dose-limiting toxicity (DLT) is defined as any AE Grade ≥ 3 attributed to ADV-043 and occurring within the DLT observation period. The DLT observation period is based on data from ongoing studies in liver-targeting gene therapy showing that treatment-related adverse events have occurred in general within 4 weeks of study treatment and have not led to long term sequelae (Pasi 2017, Dimension Therapeutics 2017).

The DLT observation period for the sentinel subject is 6 weeks (14 days plus 4 weeks) post study treatment; and for the second or any subsequent subject within the same dosing cohort, 4 weeks post study treatment. This takes into consideration the 14-day minimum interval between the sentinel subject and the second subject dosed in a cohort and the 4-week DLT observation period. The DLT observation period will be used during the review between the DMC and Adverum to make decisions related to dose escalation and cohort expansion. If a subject

withdraws from the study prior to completion of the DLT observation period, the subject will be replaced and followed for DLTs before decisions regarding cohort expansion are made.

Any AE Grade ≥ 3 attributed to ADVM-043 that occurs outside of the DLT observation period will require enrollment suspension until review and assessment of the event has taken place (Section 3.9).

Within each dosing cohort, the first DLT will result in cohort expansion from a total of 2 subjects to a total of 5 subjects. If more than one DLT occurs within the same dose cohort, the MTD will have been exceeded; de-escalation and cohort expansion of the prior cohort or an additional intermediate dose may be considered. The MTD will be the dose at which no more than 1 of the 5 subjects in an expanded cohort experiences a DLT.

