4.2 Reasons for withdrawal/discontinuation

Subjects may withdraw from the study at any time and for any reason without prejudice to their future medical care by the Investigator or at the clinical trial site. Should a subject withdraw from the study, the Investigator should ensure that the subject's clinical care is continued. Every effort should be made to retain a subject in the study in order to monitor their safety.

Should a subject withdraw their consent for specific assessments (eg, bronchoscopy, imaging, ████, blood sampling), a protocol deviation should be recorded. All other assessments should be completed as specified by the protocol.

The reason for a subject not completing the study should be recorded. A subject may be withdrawn from the study for any of the following reasons:

- 26) Subject does not meet the eligibility criteria at the Baseline Visit
- 27) Lost to follow-up
- 28) Withdrawal of consent for participation in the study
- 29) Adverse event(s) that put the safety of the subject at risk
- 30) Major protocol deviation prior to treatment. The Investigator should discuss the protocol deviation with the Medical Monitor before withdrawing the subject
- 31) Investigator decides to discontinue the subject.
- 32) Sponsor decides to discontinue the subject.

33) Other (eg, death, inability to attend scheduled clinic visits, investigational medicinal product not administered).

The Investigator is to withdraw a subject if Adverum terminates the study.

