4.3 Management of Withdrawals

Subjects are free to withdraw from the study or study treatment at any time upon request. Subject participation in the study may be stopped at any time at the discretion of the Investigator or at the request of Adverum.

When a subject withdraws from the study, the reason(s) for withdrawal are to be recorded on the electronic case report form (eCRF). Whenever possible, all subjects who withdraw from the study following treatment are to be encouraged to undergo all End-of-Study (EOS) assessments (Week 52 visit) (Section 6.4.16). The subject will be offered enrollment in a long-term follow-up study.

A subject who fails to return for EOS assessment is to be contacted by a representative from the clinical trial site in an attempt to have them complete protocol-specified assessments. Appropriate contact includes 2 documented phone calls followed by a registered letter before a subject may be listed as lost to follow up.

It is vital to obtain follow-up data on any subject who is withdrawn from the study and has an ongoing AE or SAE. In every case, efforts must be made to undertake protocol-specified safety follow-up procedures.

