4.4 Replacements

In the event that a subject withdraws prior to completion of the DLT observation window, the subject will be replaced and followed for DLT before decisions regarding subject replacement are made.

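### Protocol Section 11.2.2 requires withdrawal after any protocol deviation, but Section 4.2, which it cites, only permits withdrawal and keeps a subject who refuses one assessment in the study

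*Protocol*

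**What the plan says.** Protocol Section 11.2.2 first defines a deviation broadly, as an unplanned departure from protocol procedures. It then sets apart a more serious class: "A significant protocol deviation occurs when there is nonadherence to the protocol by the subject or Investigator" and this creates significant added risk for the subject. Its consequence, however, is attached to the broad class: "Any protocol deviation will lead to the subject being withdrawn from the study (Section 4.2".

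Protocol Section 4.2 introduces its withdrawal reasons with "A subject may be withdrawn from the study for any of the following reasons". The only reason on that list that concerns deviations is "Major protocol deviation prior to treatment", to be discussed with the Medical Monitor first. The list also includes investigator decision, sponsor decision and an open category. For a subject who withdraws consent to a specific assessment, Section 4.2 says "a protocol deviation should be recorded. All other assessments should be completed as specified by the protocol". The same section asks sites to try to keep subjects in the study for safety monitoring.

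Withdrawal has a consequence for dose escalation. Section 3.6 says that if a subject "withdraws from the study prior to completion of the DLT observation period, the subject will be replaced and followed for DLTs" before cohort-expansion decisions are made. Section 4.4 begins the same way: "In the event that a subject withdraws prior to completion of the DLT observation window, the subject will be replaced". SAP Section 5.1 repeats the rule.

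**The concern.** An investigator who turns to Section 11.2.2 is told to withdraw a subject after any deviation. One who turns to Section 4.2 is told that withdrawal is optional and, for a refused assessment, that the subject carries on. A site cannot comply with both.

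The primary objective is the safety of intravenous dosing, and SAP Section 5.1 gives 2 to 5 subjects per cohort. If Section 11.2.2 were followed as written, a minor departure would end the 52-week schedule of a subject who has already received a single-dose gene therapy. If that happened inside the dose-limiting toxicity (DLT) window, it would also bring in a replacement subject and change who is counted when the cohort is judged.

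The reporting plan might not show that the rule had been applied. The reasons for non-completion in SAP Section 6.1 follow Section 4.2 and name no post-treatment deviation. Unless a category is added, a treated subject withdrawn under Section 11.2.2 would be counted as an investigator decision, a sponsor decision or other.

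**Working it through.** **The text.** The two protocol sections compare as follows.

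| Point | Section 11.2.2 | Section 4.2 |
|---|---|---|
| Force | mandatory (*will*) | permissive (*may*) |
| Severity | any deviation | major deviation |
| Timing | no limit | before treatment |
| Subject refuses one assessment | a deviation, so withdrawn | deviation recorded, other assessments continue |

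The first three rows differ in force and scope. The fourth is a direct conflict. Reading *any* as *significant* in Section 11.2.2 does not remove the mismatch: the rule would still be mandatory and without a timing limit, while Section 4.2 is permissive and restricted to the period before treatment.

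**Illustrative size.** The plan gives no figure to reproduce, and no deviation rate is assumed. The withdrawal weeks below are examples. The early-withdrawal visit is taken to occur in that week, and visit windows are ignored.

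Inputs:
- Adverse-event reporting ends 30 days after the last study visit (Protocol Section 7.0); 30/7 = 4.3 weeks.
- Post-treatment A1AT timepoints (Protocol Section 6.4.12): Days 7, 14 and 21 (3), plus Weeks 4, 6, 8, 10, 12, 16, 20, 24, 28, 32, 40 and 52 (12); 3 + 12 = 15.

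Formulas: end of reporting = week of last visit + 4.3. Timepoints lost = 15 − timepoints up to and including the withdrawal week. For a completer, reporting ends at 52 + 4.3 = Week 56.3.

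| Withdrawn at | Reporting ends (week) | Shorter by (weeks) | A1AT timepoints lost |
|---|---|---|---|
| Week 6 | 6 + 4.3 = 10.3 | 56.3 − 10.3 = 46 | 15 − 5 = 10 |
| Week 12 | 12 + 4.3 = 16.3 | 56.3 − 16.3 = 40 | 15 − 8 = 7 |
| Week 24 | 24 + 4.3 = 28.3 | 56.3 − 28.3 = 28 | 15 − 11 = 4 |

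The timepoint losses are upper limits. Section 6.4.12 does not require A1AT samples once a subject starts protein augmentation therapy, and Section 5.4.2 allows that after Week 12. Replacement would arise only from withdrawal before the end of the DLT window, which is 6 weeks for the sentinel subject and 4 weeks for the others (Section 3.6).

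**What does not change.** Under SAP Section 5.3 the full analysis set is everyone who received any amount of ADVM-043, so a withdrawn subject's collected data stay in every summary.

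**The case against.** The best counter-argument is that this is one loosely worded sentence in an administrative section that the rest of the protocol does not follow. Section 4.2 wants subjects retained. The next paragraph of Section 11.2.2 lets an investigator deviate to remove an immediate hazard and asks for documentation and notification, not withdrawal. That makes a drafting slip likely, but the sentence remains an instruction that sites have agreed to follow.

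Second, Section 11.2.2 defines deviations as unintended or unanticipated, and a refusal is deliberate. Section 4.2 nevertheless calls the refusal a protocol deviation, so the conflict remains.

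Third, the replacement rules speak of a subject who withdraws, not one who is withdrawn. Applying them to both is an inference, though a fair one: Section 4.3 handles both under one heading.

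Fourth, the reporting problem is limited. SAP Section 6.1 leaves its disposition categories open. Disposition and deviations are both listed by cohort and subject, so in cohorts this small the two listings can be compared. The review and listing steps in SAP Sections 5.4.3 and 6.2 fit either rule; only the Section 6.1 reasons clearly follow Section 4.2. These points stand.

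Fifth, safety follow-up is partly protected. Under Section 4.3, "all subjects who withdraw from the study following treatment are to be encouraged to undergo all End-of-Study (EOS) assessments"; sites must also attempt protocol-specified safety follow-up, and the long-term study is offered. Section 7.0 has ongoing drug-related events followed until resolved or stable. This reduces the loss but does not restore the scheduled visits.

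**Conclusion.** The inconsistency is real. Section 11.2.2 cites Section 4.2 for a rule that Section 4.2 does not contain, and for a refused assessment the two give opposite instructions. Under a literal reading, and with the illustrative withdrawal weeks above, routine adverse-event reporting for the affected subject would be 46, 40 or 28 weeks shorter, and up to 10, 7 or 4 of 15 A1AT timepoints would be lost. The number of subjects affected cannot be computed from the documents.

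The sentence should be corrected, but it does not threaten the planned analyses: no analysis set or endpoint depends on it. The SAP records that Cohort 4 was not enrolled and that Part B did not proceed, so any effect on replacement may already be past. What mainly remains is for the study report to make clear what was done.

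**What to change.** Reconcile the last sentence of the first paragraph of Protocol Section 11.2.2 with Section 4.2 so that a single rule applies. Which rule that is remains the sponsor's decision. If Section 4.2 is meant to govern, it is enough to delete the sentence or replace it with a cross-reference to the Section 4.2 reasons. If Section 11.2.2 is meant to govern, Section 4.2 and the non-completion reasons in SAP Section 6.1 would have to be brought into line with it.

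Whether or not the protocol is amended again, the study report should state which rule was applied and whether any treated subject was withdrawn or replaced because of a deviation.

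If Section 4.2 governs, the cost is one protocol sentence and one statement in the report, with no change to any analysis set, endpoint or planned table.

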11.3 Study Termination

Adverum Biotechnologies, Inc., has every intention of completing the study. However, Adverum is authorized to terminate the study at any time for clinical or administrative reasons.

11.4 Final Report

Whether the study is completed or prematurely terminated, Adverum will ensure that the clinical study reports (CSR) are prepared and provided to the regulatory agencies as required. Adverum will also ensure that the CSR in marketing applications meet the standards of the ICH Harmonised Tripartite Guideline E3: Structure and Content of Clinical Study Reports.

Where indicated by regulatory requirements, an Investigator signatory will be identified for the approval of the CSR. The Investigator is to be provided reasonable access to statistical tables, figures, and relevant reports and will have the opportunity to review the complete study results.

Upon completion of the CSR, Adverum is to provide the investigator with the summary of the study results. The investigator is encouraged to share the summary results with the study subjects, as appropriate. The study results will be posted on publicly available clinical trial registers.

13.0 APPENDICES

13.1 Schedule of Assessments ADVM-043-01 Protocol Amendment 7 Part A and Part B

Note: Unless specified, all procedures listed below are to be performed for both Part A and Part B

Procedure	Pretreatment		TX	Follow-up ¹⁰																				
	Week	Week		0	1				2	3	4	6	8	10	12	14	15	16	18	20	24	28	32	40
Visit number	1	2	3	4	5	6	7	8	9	10	11								12					13
Visit Day	Screening	-1	0	1	2	3	7	14	21															
Visit schedule/window	█	█	█	█	█	█	█	█	█	█	█	█	█	█	█	█	█	█	█	█	█	█	█	█
Informed consent	X																							
Demography	X																							
Medical history	X																							
Inclusion/Exclusion Criteria	X	X																						
Physical exam	X	X																						X
Abbreviated physical exam				X			X			X		X		X					X					
Vital signs	X	X	X	X	X	X	X			X		X		X					X					X
Height	X																							
Weight	X																		X					X
ECG	X																							X
Sample for A1AT genotype ¹	X																							
█	█	█					█			█				█					█					█

Procedure		Pretreatment		TX	Follow-up ¹⁰																			
Week				0	1			2	3	4	6	8	10	12	14	15	16	18	20	24	28	32	40	52
Visit number		1	2	3	4	5	6	7	8		9		10		11					12				13
Visit Day		Screening	-1	0	1	2	3	7	14	21														
Visit schedule/window		█	█	█	█	█	█	█	█	█	█	█	█	█	█	█	█	█	█	█	█	█	█	█
█		█	█	█	█	█	█	█	█	█	█	█	█	█	█	█	█	█	█	█	█	█	█	█
Sample for total A1AT level (NephelometryTotal) ³		X						X																
Sample for A1AT levels (total & M-type) & function ³			X					X	X	X	X	X	X	X	X	X	X	X	X	X	X	X	X	X
█		█																						
Chest x-ray		X																						
Hepatic ultrasound		X																						
Clinical laboratory tests ⁴		X	X		X	X		X			X			X						X				X
HIV, HBV, HCV serology ⁵		X																						
Pregnancy test ⁶		X	X																					X
Part B only	Bronchoscopy & lung ELF sample for A1AT levels and function ⁷	X									X									X				

Procedure	Pretreatment		TX	Follow-up ¹⁰																				
	Week			0	1				2	3	4	6	8	10	12	14	15	16	18	20	24	28	32	40
Visit number	1	2	3	4	5	6	7	8		9		10		11						12				13
Visit Day	Screening	-1	0	1	2	3	7	14	21															
Visit schedule/window	█	█	█	█	█	█	█	█	█	█	█	█	█	█	█	█	█	█	█	█	█	█	█	█
█	█	█	█	█	█	█	█	█	█	█	█	█	█	█	█	█	█	█	█	█	█	█	█	█
█	█	█	█	█	█	█	█	█	█	█	█	█	█	█	█	█	█	█	█	█	█	█	█	█
ADVM-043 administration ⁸			X																					
Concomitant medications	X	X	X	X	X	X	X	X		X		X		X						X				X
AEs ⁹	X	X	X	X	X	X	X	X		X		X		X						X				X
█	█	█	█	█	█	█	█	█	█	█	█	█	█	█	█	█	█	█	█	█	█	█	█	█
ALT, AST		X ¹¹																		X	X	X	X	X

Note: X, mandatory procedure; (X), Investigator discretion.

Abbreviations: A1AT=alpha-1 antitrypsin; AAV=adeno-associated virus; █; AE=adverse event; ALT=alanine aminotransferase; AST=aspartate aminotransferase; BAL=bronchial alveolar lavage; BL=baseline; ECG=12-lead electrocardiogram; ELF=epithelial lining fluid; HIV=human immunodeficiency virus; HBV=hepatitis B virus; HCV=hepatitis C virus; SAE=serious adverse event; TX=treatment; Unsch=unscheduled visit.

- 1 Only subjects with genotype ZZ or ZNull are eligible. Genotyping is not required for subjects with documented evidence of genotype.
- 2 Perform as one of first screening assessments.

- 3 Sample for total A1AT level to be collected after a minimum 8-week washout period for subjects receiving protein augmentation therapy (PAT) at the Screening Visit. For subjects who resume or start PAT post-treatment, samples for A1AT levels will not continue to be obtained; however, all other safety related parameters (ie, clinical laboratory tests, LFTs [REDACTED] and assessment of AEs) will continue to be collected according to the schedule of assessments.
- 4 [REDACTED] Analysis will be done by the central laboratory.
- 5 Serology includes: HIV; HBV surface antigen; HCV RNA. Analysis is to be done by the central laboratory.
- 6 Serum pregnancy test for women of childbearing potential will be performed at Screening; and a urine pregnancy test will be performed at the Baseline and Week 52 visits.
- 7 Bronchoscopy and BAL will only be performed in Part B.
- 8 ADVM-043 will be administered by IV infusion in Part-A and by intrapleural injection in Part-B.
- 9 SAEs that are observed or reported prior to treatment administration should be recorded as SAEs if they are associated with protocol-mandated interventions (invasive procedures such as medication washout, bronchoscopy, or BAL). See Section 7.0 for AE reporting details.
- 10 Unscheduled visit assessments will be performed at the discretion of the Investigator to ensure the safety of the subject
- 11 To be performed by the local lab. Treatment may be administered only after test results are available and the LFTs are within the normal range; and the uring pregnancy (if needed) is negative.
- 12 Blood samples for liver funtion testing (ALT/AST) will be collected at the following frequency:
 - twice weekly from Day 7 to Week 14 post-treatment
 - once at Weeks 15, 16, 18, 20, 24, 28, 32, 40, and 52

